3. INVESTIGATIONAL PLAN

3.1. Study design

3.1.1. Design and methodology

This study is an **open-label** study aiming at evaluating the long-term safety and the efficacy profile of ABX464 given once a day (o.d) at 50 mg in subjects who have been previously enrolled in the ABX464-101 clinical study (induction study) and who are willing to continue their treatment.

All subjects will receive ABX464 given at 50 mg o.d irrespective of their previous treatment received in the ABX464-101 study (i.e. ABX464 or Placebo).

The actual treatment received by a subject throughout the previous study (ABX464-101) will not be known at the time the subjects enter this follow-up study.

The enrolment in this follow-up study will be based on the willingness of the subject to carry on his/her participation and also based on investigator's judgement.

Subjects will be treated with ABX464 for an overall period of 48 months. Subjects will be followed up weekly during the first month, every two weeks during the second month and then on a monthly basis until M24, then quarterly from M24 to M48.

At M48, depending on their clinical response, eligible patients willing to continue study treatment will be offered to take part into a long term follow up study (ABX464-108 study). ABX464-108 study is a separate study requiring health authorities and ethics committees' approval. If patients are not eligible to pursue treatment in this long-term follow-up study, they will be followed for 4 additional weeks for safety purposes before End of study Visit.

3.1.2. Data Safety Monitoring Board – Independent Cardiovascular Safety Committee (ICVSC)

An independent Data Safety Monitoring Board (DSMB), with expertise and experience in the pathology, and without direct involvement in the conduct of the trial, will be set up specifically to guarantee effective protection of subjects, ensure the ethical conduct of the trial, benefit/risk ratio of the trial, and to ensure the independent review of the scientific results during the trial and at the end of the trial.

The DSMB will meet on a monthly basis until December 2019 and then quarterly from January 2020 onwards. Besides, the DSMB may recommend the early termination of the trial at any time if an unacceptable toxicity occurs.

In addition, DSMB will be review all potential causally related Serious Adverse Events within 7 days of the initial report.

The DSMB has only a consultative role; it will inform the sponsor who will decide whether the DSMB recommendation will be followed. A DSMB charter must be available upon submission of the trial (initial protocol) to the respective competent authorities.

An Independent Cardiovascular Safety Committee (ICVSC), comprised of 3 cardiologists with experience from drug development, will be formed as detailed in the Charter. The ICVSC will be responsible for an on-going evaluation of cardiac adverse events of special interest (Cardiac AESIs), for treatment emergent echocardiographic findings, and for treatment emergent changes of cardiac safety biomarkers (as detailed above). The ICVSC will review cardiac adverse events on an on-going basis, meet regularly and provide recommendations to Sponsor and DSMB regarding study procedures and conduct.

3.2. Duration of study participation

Subjects will be enrolled in the present study at Day 0 and will be treated for a treatment overall duration of 48 months.

From ABX464 treatment stop onwards, subjects will be followed-up for one additional month.

4. STUDY POPULATION

4.1. Number of Subjects/Centers

These subjects were enrolled in some of the active sites of the induction study (ABX464-101). These sites are located in, Belgium, Poland and Hungary.

4.2. Eligibility Criteria

4.2.1. Inclusion Criteria

A subject will be eligible for inclusion in this study only if ALL of the following criteria apply:

- Subjects previously enrolled in the ABX464-101 clinical study who have completed the initial 2-month treatment phase;
- Subjects able and willing to comply with study visits and procedures;
- Subjects with hematological and biochemical laboratory parameters as follows at the D56 visit of the ABX464-101 study:
 - Hemoglobin > 9.0 g dL-1;
 - Absolute neutrophil count $\geq 750 \text{ mm}^{-3}$;
 - Platelets $\geq 100,000 \text{ mm}^{-3}$;
 - Total serum creatinine $\leq 1.3 \times \text{ULN}$ (upper limit of normal);
 - Creatinine clearance $> 50 \text{ mL min}^{-1}$ by the Cockcroft-Gault equation;
 - Total serum bilirubin $< 1.5 \times \text{ULN}$;
 - Alkaline phosphatase, AST (SGOT) and ALT (SGPT) $< 1.5 \times \text{ULN}$;
- Subjects should understand, sign and date the written voluntary informed consent form at the enrolment visit prior to any protocol-specific procedures being performed;
- Females and males receiving the study treatment and their partners must agree to use a highly effective contraceptive method during the study and for 6 months after end of study or early termination. Contraception should be in place at least 3 months prior to study participation. Women must be surgically sterile or if of childbearing potential must use a highly effective contraceptive method. Women of childbearing potential (WOCBP) will enter the study after confirmed menstrual period and a negative pregnancy test. Highly effective methods of contraception include true abstinence, intrauterine device (IUD) or hormonal contraception aiming at inhibition of ovulation, intrauterine hormone releasing system, bilateral tubal ligation, vasectomized partner. True abstinence is defined when this is in line with the preferred and usual lifestyle of the patient. In each case of delayed menstrual period (over one month between menstruations) confirmation of absence of pregnancy is required. This recommendation also applies to WOCBP with an infrequent or irregular menstrual cycle. Female and male patients must not be planning pregnancy during the trial and for 6 months post completion of their participation in the trial. In addition, male participants should use condoms and should not donate sperm as long as contraception is required.

4.2.2. Exclusion Criteria

The following criterion should be checked at the time of screening. If this exclusion criterion applies, the subject will not be included in the study:

- Any condition, which in the opinion of the investigator, could compromise the subject's safety or the adherence to the study protocol.

5. STUDY ASSESSMENTS AND PROCEDURES

5.1. Study Flow Chart

A detailed study flow chart (with all assessments) is displayed hereafter.

	(D56) D0	D7	D14	D21	D28	D42	Day56/M2	Mx+1 to M24	M27 to M45*	M48	EoS
Time Window		± 2 days	± 2 days	± 2 days	± 4 days	± 2 days	± 4 days	± 4 days	± 14 days	± 14 days	28 days after ABX464 Stop (± 4 days)
ABX464-101 D56 examinations	X										
Obtained Inform Consent	X										
Check of IN/EX Criteria	X										
Physical Examination		X	X	X	X	X	X	X	X	X	X
Body Weight (kg)	X	X	X	X	X	X	X	X	X	X	X
Vital signs		X	X	X	X	X	X	X	X	X	X
ECG (12 lead)							X	At Month 24	X	X	X
Blood Pregnancy test (WOCBP)					X		X	X	X ^a	X ^a	X
Hematology + Biochemistry, including NT-proBNP ^b		X	X	X	X	X	X	X	X ^b	X ^b	X ^b
miR-124 blood sample (Paxgene®)								At Month 12	At Month 36	At Month 48	
Mayo score (Total or Partial)		X	X	X	X	X	X	X	X	X	X
Faecal calprotectin					X		X	X	X	X	X
Sigmoidoscopy					As needed		X	At Month 24	At Month 36	At Month 48 ^d	
Cardiac ischemic disease/congestive heart failure medical/treatment history review									X	X	
Echocardiography ^c									X	X	
SF-36 (Questionnaire)					X		X	X			
ABX464 treatment dispensation	X				X		X	X	X		
Adverse Events and CM recording	X	X	X	X	X	X	X	X	X	X	X

* Visits are performed quarterly after M24 (at M27, M30, M33, M36, M39, M42, M45, M48).

^a Urine pregnancy tests will be provided to WOCBP to perform a pregnancy check every month (between onsite visits)

^b NT-proBNP blood levels only at Month 42 and 48 and at the End of Study Visit

^c Echocardiography at the earliest visit, then at Month 42 and 48

^d Local reading result of sigmoidoscopy need to be available on M48 visit to check eligibility to enter study ABX464-108

5.2. Study conduct

It is the investigator's responsibility to ensure that all the assessments are carried out during each visit and that the intervals between visits/follow-ups are adhered to.

5.2.1. Day 0 (D56 visit of the ABX464-101 study)

The subject will be informed about the general aspects of the study and will sign the screening informed consent form. The subject number will be allocated once the subject will be created in the eCRF. Only when consent has been given may further study procedures be carried out. During Day 0 visit, the assessments planned as the D56 Visit in the ABX464-101 study protocol should be performed.

In addition, if the subject is eligible for the Follow-up study the following examination should be performed:

- Signed informed consent form;
- Inclusion/exclusion criteria will be verified globally;
- ABX464 IMP dispensation;
- Adverse Events and Concomitant Medications reporting.

5.2.2. Day 7, 14, 21, 42 visits (\pm 2 days)

The following examinations/procedures should be performed:

- Physical examination and vital signs;
- Body weight;
- Hematology & Biochemistry;
- Partial Mayo Score;
- Adverse Events and Concomitant Medications reporting;
- Schedule next subject visits.

5.2.3. Day 28, Day 56/M2, Mx+1 Visits (28 \pm 4 days) until M24

The following examinations/procedures should be performed:

- SF-36 questionnaire (as the first visit procedure);
- Physical examination and vital signs;
- Body weight;
- Hematology and Biochemistry including blood pregnancy test for all women of childbearing potential;
- Faecal calprotectin dosage;
- Sigmoidoscopy, mandatory only at D56 and at M24
- 12 leads ECG only at D56 and at M24;
- Blood sampling for miR-124 expression at month 12 only;
- Partial or Total Mayo Score;
- ABX464 IMP dispensation
- Adverse Events and Concomitant Medications reporting;
- Schedule next subject visits.

5.2.4. M27 until M45 (Calendar month \pm 14 days)

Visits are performed quarterly after M24. Only 7 visits should be performed at M27, M30, M33, M36, M39, M42, and M45. The following examinations/procedures should be performed:

- Review of the subject's medical history at the earliest opportunity to discontinue subjects with history of cardiac ischemic disease and/or congestive heart failure; If the patient needs to be discontinued, she/he will perform the End of Study Visit 4 weeks after last study drug intake.
- Physical examination and vital signs;
- Body weight;
- Hematology and Biochemistry including blood pregnancy test for all women of childbearing potential and NT-proBNP (at Month 42 only);
- Faecal calprotectin dosage;
- 12 leads ECG;
- Blood sampling for miR-124 expression at month 36 only
- Partial Mayo Score;
- Total mayo score (only at M36);
- ABX464 IMP dispensation;
- Adverse Events and Concomitant Medications reporting;
- Sigmoidoscopy, mandatory at M36;
- Echocardiography at the earliest visit, and at M42;

- Schedule next subject visits.

5.2.5. M48 (Calendar month ± 14 days)

Visit M48 is the last visit in this study before entering the long-term follow-up study ABX464-108. If the patient is not eligible to enter this ABX464-108 study, she/he will perform the End of Study Visit (EoS) 4 weeks after last study drug intake.

The following examinations/procedures should be performed:

- Physical examination and vital signs;
- Body weight;
- Hematology and Biochemistry including blood pregnancy test for all women of childbearing potential and NT-proBNP;
- Faecal calprotectin dosage;
- 12 leads ECG;
- Blood sampling for miR-124 expression
- Partial Mayo Score;
- Total mayo score;
- Adverse Events and Concomitant Medications reporting;
- Sigmoidoscopy, mandatory;
- Echocardiography
- Schedule the EoS visit (if patient doesn't enter the study ABX464-108)

Nota bene:

- **The last treatment intake in study ABX464-102 should be the day before this visit M48.**
- **The local reading result of sigmoidoscopy need to be available on M48 visit to check eligibility to enter study ABX464-108.** The sigmoidoscopy can be performed within 14 days before the visit but not after the visit. If the sigmoidoscopy results (local reading) are not available on M48, the patient will be considered not eligible to enter the ABX464-108 study and will performed the end of study visit 28 days (+4 days) after M48.

5.2.6. End of Study Visits

This EoS visit should be performed 28 days (+4 days) after the last study treatment dosing, or if a subject meets a discontinuation criterion before. From the last dosing day, subjects will be treated according to standard of care.

Following examinations/procedures should be performed:

- Physical examination and vital signs;
- Body weight;
- Hematology and Biochemistry including blood pregnancy test for all women of childbearing potential and NT-proBNP;
- Partial Mayo Score;
- 12 leads ECG;
- Faecal calprotectin dosage;
- Adverse Events and Concomitant Medications reporting.

NB: In case of premature discontinuation occurring during the treatment phase the above examinations should be performed as an End of Study Visit 4 weeks after treatment interruption.

After the end of study visit, patients will be treated according to the local standard of care.

5.3. Detail of the study assessments

5.3.1. Echocardiography

Since enrolment is completed at the time of this amendment, drug-free baseline measurements are not available.

All patients ongoing in the study have already undergone Month 36 visit. Therefore, an echocardiography will be performed at the earliest visit and then at Month 42 and Month 48. Echocardiography will be performed locally. Procedures will be standardized for optimized video acquisition at clinical sites. Sites will receive an Echocardiography Manual that includes detailed instructions regarding image acquisition.

Two-dimensional echocardiography measurements will be assessed during the study. The following standard parameters - pertinent to the assessment of changes in cardiac function will be assessed:

- Left Ventricular Ejection Fraction (LVEF%)
- Left Ventricular end systolic/end diastolic volumes
- Left Ventricular septal/posterior wall thickness
- Left Ventricular Mass/Mass indexed
- Left Ventricular Global Longitudinal Strain (GLS)
- Left Atrial volume
- Doppler assessment (Mitral E/A ratio, Stroke Volume, Cardiac Output, Tissue Doppler Imaging)
- Valvular assessment for regurgitation/stenosis
- Right ventricular size

Specific attention will be brought to potential changes from previous assessment in LVEF and GLS. All echocardiographic parameters will be presented descriptively and will be reviewed by the Independent Cardiovascular Safety Committee (ICVSC).

5.3.2. Cardiac ischemic disease/congestive heart failure) medical / treatment history review

- A retrospective review of medical history to search for cardiac ischemic disease and/or congestive heart failure will be done at the next possible visit of the subject as enrolment is finished at the time of this amendment. Patients with a history of or treated for cardiac ischemic disease and/or congestive heart failure will have to be discontinued from the study. If the patient needs to be discontinued, she/he will perform the End of Study Visit 4 weeks after last study drug administration and will then be treated according to the standard of care upon study treatment interruption.

5.3.3. Physical Examination and Vital Signs

A routine physical examination (including body weight) will be done at each study visit. Physical examinations will cover eyes, ears, nose, throat, lungs/thorax, heart/cardiovascular system, abdomen, skin and mucosae, nervous system, lymph nodes, musculo-skeletal system, and, if applicable, others. Any new clinically relevant finding compared to baseline must be documented as adverse event.

Measurements of vital signs will be done at each visit (Blood pressure, Heart Rate, Body temperature). The subject should rest supine for at least 10 minutes prior to measurements. The measurements can be performed either in sitting or supine position of the subject. The right or left arm may be used. However, the position and the arm used for measurement should be kept constant throughout the trial for an individual subject.

The investigator should ensure that each parameter outside the normal range is assessed for clinical significance. For any deviation assessed clinically significant, the investigator has to document the change as an adverse event (AE) in the eCRF.

In addition, it is at the discretion of the investigator to document any change or trend over time in vital signs as an AE if he considers the change to be clinically significant, even if the absolute value is within the alert limit or reference range.

5.3.4. Pregnancy

For all female subjects of childbearing potential, a blood pregnancy test (beta human chorionic gonadotropin [HCG]) will be each month and quarterly after Month 24. From Month 24 onwards, monthly urine pregnancy test will be provided to WOCBP to check for pregnancy between on-site visits. In case of positive pregnancy testing, detailed procedures can be found in section 8.4.2.

5.3.5. ECG

Electrocardiograms have to be done at Day 56, quarterly from M24 to M48 and at EoS visits. At least a 12-lead ECG with recordings of at least 6 action potentials in lead II (paper speed 25mm/s, amplitude 10mm/mV) has to be done in a resting position. Prior to the recording the subject should be at rest for at least five minutes. Resting ECG should be performed before any examinations.

The ECG printout will be reviewed by the investigator and a signed and dated copy of the ECG will be attached to the medical file. The original ECG printouts are considered as source data and should be stored at site. In case thermal paper is used, a copy of the original ECG must be kept as well. All abnormal findings must be documented in the CRF. Any clinically relevant findings compared to ECG done at the EoS visit of the previous study (ABX464-101) must be documented as adverse events.

5.3.6. miR-124 expression level determination

ABX464 up-regulates miRNA in PBMCs, making of this micro-RNA a potentially useful biomarker for ABX464 treatment monitoring. Determination of miRNA level in total blood will be performed at Month 12, Month 36 and Month 48 in order to assess the sustainability of the up regulation observed during the induction study. Assays for miRNA determination will be conducted by a specialized central laboratory.

Total blood in PAXgene® tubes will be used according to lab manual instructions.

5.3.7. SF-36 questionnaire (SF-36)

The SF-36 questionnaire is a self-administered questionnaire containing 36 items which takes about five minutes to complete. It measures health on eight multi-item dimensions, covering functional status, well-being, and overall evaluation of health. SF-36 will be filled in by the subjects on a monthly basis until M24 prior to any study procedures.

5.3.8. Partial/Total Mayo Score

The Total Mayo score is the most commonly used index in clinical trials and consists of 4 items: stool frequency, rectal bleeding, flexible sigmoidoscopic examination, and a physician global assessment of disease activity (Appendix#3).

A non-invasive 9-point Mayo or partial Mayo Score (pMS) incorporates stool frequency, rectal bleeding, and the physician's global assessment of disease activity. The partial Mayo Score has been found to correlate closely with the full Mayo score and to independently have strong discriminative and construct validity and responsiveness to change in disease activity.

Modified Mayo Score (MMS) consists of 3 items: stool frequency, rectal bleeding, flexible sigmoidoscopic examination) and partial Modified Mayo Score (pMMS) consists of only 2 items: stool frequency and rectal bleeding. Either the Partial or the Total Mayo score will be completed at each subject visit by the Investigator.

Partial modified or modified Mayo score will also be used in descriptive analysis and for efficacy evaluation.

5.3.9. Sigmoidoscopy

A Sigmoidoscopy will be performed in all subjects at Day 56/M2, Month 24, Month 36, and Month 48 (i.e. Study procedure).

In addition, monthly sigmoidoscopies could be performed if deemed necessary by the investigator (Until month 24). In such a case, the endoscopy rating will be reported in the eCRF (Total MCS).

Sigmoidoscopies procedures (or colonoscopies if applicable) at Month 24, Month 36, and Month 48 will be standardized for optimized video acquisition at clinical sites. Sigmoidoscopies should be performed according to the Central Imaging Management System Charter. Central Imaging Management System will be provided including a central image database. Once uploaded, video data will be analyzed for quality and resolution prior to independent review by an expert central reader. Study videos will be scored separately using the Mayo Clinic Score (excluding friability) for all time points by central readers.

The local reading result of sigmoidoscopy need to be available on M48 visit to check eligibility to enter study ABX464-108. The sigmoidoscopy can be performed within 14 days before the visit but not after the visit. If the sigmoidoscopy results (local reading) are not available on M48, the patient will be considered not eligible to enter the ABX464-108 study and will performed the end of study visit 28 days (+4 days) after M48.

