Fecal Calprotectin (µg/g)	All patients	-1027.7	-2192.8 **	-2316.8 **
Mean change from baseline				-2280.9 **
**p-values of <0.01 versus placebo (MMRM)				
1 = Intent-to-treat patient population. Drop-out patients were considered as failure for all binary endpoints. Nearest neighbor imputation (as defined in the Statistical Analysis Plan) was used for missing values at week 8 and applied to MMS, clinical remission, and clinical response. Endoscopic improvement rates are presented without imputation (data available at time point).				
a = Endoscopic improvement is defined as endoscopic subscore ≤1.				
b = Clinical remission (per Modified Mayo Score) is defined as stool frequency subscore (SFS) ≤1, rectal bleeding subscore (RBS) of 0 and endoscopic subscore ≤1.				
c = Clinical response (per Modified Mayo Score) is defined as a decrease from baseline in the Modified Mayo Score ≥2 points and ≥30% from baseline, plus a decrease in RBS ≥1 or an absolute RBS ≤1.				
d = Evidence of friability during endoscopy confers an endoscopic subscore of 2 or 3				

ABX464 was shown to be effective in patients refractory to conventional treatments and, importantly, also in patients with inadequate response, loss of response, or intolerance to biologics and/or JAK inhibitors. These efficacy results warrant the continuation of the development of ABX464 in UC indication.

97.7% of all patients who completed the phase 2b induction study (ABX464-103), irrespective of treatments or treatment outcome during the induction study, enrolled into this subsequent open-label maintenance study to evaluate the long-term safety and efficacy profile of ABX464 for up to two years.

Clinical Safety

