5.3.10. Clinical remission, clinical response, and corticosteroid-free clinical remission

The following remission and response will be assessed at M12, M24, M36 and M48:

Clinical remission is achieved when all the following criteria are met in the components of the Mayo Score:

- rectal bleeding sub-score = 0
- central endoscopy sub-score <= 1
- stool frequency sub-score <= 1.

Clinical response is defined as:

- reduction in Total Mayo Score of at least 2 points and >= 30 percent from baseline
- with an accompanying decrease in rectal bleeding sub-score of >= 1 point or absolute rectal bleeding sub-score of <= 1 point.

Corticosteroid-free clinical remission is defined as clinical remission at M12, M24, M36 and M48, and concomitant corticosteroid free for ≥ 12 weeks prior to these timepoints among patients with clinical remission after 8 weeks of induction treatment (at baseline of ABX464-102 study).

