Appendix 3: Mayo Score (Ulcerative Colitis)

Components of the Mayo Score	
Stool frequency	
0	Normal
1	1–2 stools/day more than normal
2	3–4 stools/day more than normal
3	5 or more stools/day more than normal
Rectal bleeding	
0	None
1	Visible blood with stool less than half the time
2	Visible blood with stool half of the time or more
3	Passing blood alone
Mucosal appearance at endoscopy	
0	Normal or inactive disease
1	Mild disease (erythema, decreased vascular pattern, mild friability)
2	Moderate disease (marked erythema, absent vascular pattern, friability, erosions)
3	Severe disease (spontaneous bleeding, ulceration)
Physician rating of disease activity	
0	Normal
1	Mild
2	Moderate
3	Severe

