#### 11.3.1.1 Mayo Score

The **Total Mayo score** (TMS) consists of 4 items: stool frequency, rectal bleeding, flexible sigmoidoscopic examination, and a physician global assessment of disease activity (see protocol Appendix 3).

A non-invasive 9-point Mayo or **partial Mayo Score** (pMS) incorporates stool frequency, rectal bleeding, and the physician's global assessment of disease activity. The partial Mayo Score has been found to correlate closely with the full Mayo score and to independently have strong discriminative and construct validity and responsiveness to change in disease activity. Either the Partial or the Total Mayo score will be completed at each subject visit by the Investigator.

**Modified Mayo Score** (MMS) consists of 3 items: stool frequency, rectal bleeding, flexible sigmoidoscopic examination.

**Partial Modified Mayo Score** (pMMS) consists of only 2 items: stool frequency and rectal bleeding. MMS or pMMS will also be used in descriptive analysis and for efficacy evaluation.

Absolute values and change from BIS and from BOLS to each post BOLS timepoint will be presented using descriptive statistics for Total Mayo Score (TMS), Partial Mayo Score (pMS), Modified Mayo Score (MMS) and partial Modified Mayo Score (pMMS) (*Table 14.2.1.1 and 14.2.1.2*) and for the different components of the Total Mayo Score (stool frequency, rectal bleeding, physician rating of disease activity and mucosal appearance at endoscopy – central reading) (*Table 14.2.1.3 and 14.2.1.4*).

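### Clinical remission may rest on a central or a local endoscopy reading although the two use differently described scales, and the reading behind the Total and Modified Mayo Scores is not named

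*Protocol*

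**What the plan says.** **Two scale descriptions.** Protocol Appendix 3 defines endoscopic sub-score 1 as "Mild disease (erythema, decreased vascular pattern, mild friability" and sub-score 2 as "Moderate disease (marked erythema, absent vascular pattern, friability, erosions". SAP section 11.3.1.1 points to that appendix when it defines the Total Mayo Score (TMS): "flexible sigmoidoscopic examination, and a physician global assessment of disease activity (see protocol Appendix 3". For the central readers, Protocol section 5.3.9 says: "Study videos will be scored separately using the Mayo Clinic Score (excluding friability) for all time points by central readers". The wording of that modified scale appears in neither document.

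**Which scopes are set up for central reading.** Protocol section 5.3.9: "Sigmoidoscopies procedures (or colonoscopies if applicable) at Month 24, Month 36, and Month 48 will be standardized for optimized video acquisition at clinical sites". Before M24, Protocol section 5.2.3 asks for "Sigmoidoscopy, mandatory only at D56 and at M24". Other scopes up to M24 are at the investigator's discretion, with the rating entered in the eCRF. No scope is mandatory at M12.

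**Clinical remission.** Protocol section 5.3.10 requires "central endoscopy sub-score <= 1". SAP section 11.3.1.6 accepts a sub-score of at most 1 from either reader and does not rank them. SAP section 1.2 lists the departures from the protocol, including changes to clinical response and to corticosteroid-free remission, but not this one.

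**Other endpoints.** Endoscopic improvement and endoscopic remission use the central sub-score in Protocol section 5.3.11 and SAP section 11.3.1.7. TMS and the Modified Mayo Score (MMS) carry no statement of which reading they use.

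**The concern.** The remission cut-off lies between sub-scores 1 and 2. Appendix 3 places mild friability just below that cut-off, and friability is the feature the central readers treat differently. A rule that accepts either reading therefore lets the same mucosa count as remission or not, depending on which score is picked up. As the SAP is worded, a patient with local sub-score 1 and central sub-score 2 at M24, M36 or M48 can be counted as in remission, although the protocol's definition would not count that patient.

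The same choice runs over time. Sustained and corticosteroid-free remission and the remission shift tables compare a visit with the open-label baseline (BOLS) or the induction baseline (BIS). If the two ends come from different readers, a change of scale can pass for a change in disease, or hide one. Durability of remission is a main long-term efficacy result here, and it rests on 22 enrolled patients.

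**Working it through.** There is no sample-size or power figure to reproduce. The check traces the reading behind each output and then sizes one reclassified patient.

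**1. Reading behind each output**

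| Output | Protocol | SAP | Can scales mix? |
|---|---|---|---|
| Clinical remission and its shift tables | Central (5.3.10) | Either reader, unranked (11.3.1.6) | Yes, by the rule as written |
| Corticosteroid-free and sustained clinical remission | Built on remission (sustained version added by the SAP) | Built on remission at the visit and at BOLS (11.3.1.6, 11.3.1.8) | Yes, inherited |
| TMS, MMS, clinical response | Not named; the investigator completes the score (5.3.8) | Not named (11.3.1.1, 11.3.1.6) | Possible, not established |
| Change in the endoscopy component | Not specified | Central (11.3.1.1) | Not among M24, M36, M48; BIS and BOLS readings not stated |
| Endoscopic improvement, endoscopic remission | Central (5.3.11) | Central (11.3.1.7; footnote to Table 14.2.6.1) | No at M24, M36, M48; no central video process described for M12 |
| Sustained endoscopic versions | Not in the protocol | Paired with BOLS (11.3.1.8) | BOLS reading not stated |

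Listing 16.2.6.1 has separate columns for central and local sub-scores but one column each for TMS and MMS, so one reading must be chosen without a stated rule. Two further SAP rules can bring an early or unscheduled score into a scheduled visit: substitution of the closest unscheduled endoscopy within one month (section 11.3) and last observation carried forward for continuous scores (section 10.4).

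**2. What the scale difference does.** Take mucosa scored 1 on Appendix 3 because of mild friability.
- If the central scale moves friability to 2 or higher, the score crosses the cut-off. Remission on that reading is lost, and TMS and MMS rise by at least 1.
- If the central scale ignores friability, the score is 1 or 0. It stays within the cut-off, so remission is unchanged; only sub-score 0 (endoscopic remission) and the Mayo totals can move.

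The documents do not say which applies.

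**3. Size of one reclassification.** Inputs from Protocol section 1.3: 15 + 7 = 22 enrolled; 16 scoped at M12, all with sub-score 0 or 1; 12 of the 16 in remission. The reader behind these interim figures is not stated.
- 1/16 = 6.25 points; 1/22 = 4.5 points.
- If k of the 12 remitters were rescored from 1 to 2 (k is an assumption; the true number is unknown):

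| k | (12 − k)/16 | (12 − k)/22 |
|---|---|---|
| 0 | 75.0% | 54.5% |
| 1 | 68.75% | 50.0% |
| 2 | 62.5% | 45.5% |
| 3 | 56.25% | 40.9% |
| 4 | 50.0% | 36.4% |

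Under the second meaning in step 2, only the k = 0 row applies.

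**4. Consistency at M12.** On a single reading, remission implies endoscopic improvement, because both need a sub-score of at most 1. Suppose no central reading exists at M12. Improvement is then missing in the observed-cases analysis and counts as failure for all 22 patients under non-responder imputation (0/22). Clinical remission could still be counted from local scores, for example 12/22 = 54.5%. One report would then show remission without endoscopic improvement.

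**The case against.** The best defence is that the SAP's either-reader wording is a fallback: central where it exists, local where it does not. That is sensible, but it is not written, and it would still pair readings from different readers in the sustained and shift analyses. The Central Imaging Management System Charter, which Protocol section 5.3.9 cites, may define the modified scale; it is not among the documents, and the SAP does not draw on it. Listing 16.2.6.1 shows both sub-scores, so discordance would be visible, but only patient by patient.

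Several stronger readings are tempting and are not supported:
- **That endoscopic improvement and endoscopic remission mix scales.** Both are central-only in both documents. For the same reason, one cannot recast the 16/16 with sub-score 0 or 1 at M12 as a lower improvement rate through friability: a local M12 score does not feed improvement at all.
- **That central reading turns a mildly friable 1 into a 2.** The statement "Evidence of friability during endoscopy confers an endoscopic subscore of 2 or 3" is a footnote to the ABX464-103 results in Protocol section 1.2.5. It does not define the scale for this study.
- **That all scopes before M24 were scored only on Appendix 3.** Section 5.3.9 ties standardised acquisition to M24, M36 and M48 but also says central scoring covers all time points. Local-only scoring of earlier scopes is an inference.
- **That a false worsening would appear between M12 and M24.** No such change is planned; changes run from BIS and BOLS.

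It also stands that these endpoints are secondary and descriptive.

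**Conclusion.** The point holds for clinical remission and everything built on it. The SAP permits two readers with differently described scales, without a hierarchy, against a protocol definition that is central-only, and does not declare the change. For TMS, MMS and clinical response, mixing is possible but not shown. For endoscopic improvement and endoscopic remission the gap is narrower: no central reading is described for M12 or for the BOLS value used in the sustained versions.

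Each reclassified patient is worth 6.25 points on the 16 scoped at M12 or 4.5 points on the 22 enrolled. The total effect and its direction cannot be given, because the number of mildly friable readings, the central scale's wording and the reader at BIS and BOLS are all unstated. The primary endpoint, treatment-emergent adverse events, is not touched. The plan should be corrected before database lock, but this does not threaten the study's main purpose.

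**What to change.** 1. State the wording of the central scale, including how friable mucosa is scored, and reconcile Protocol Appendix 3 with section 5.3.9.
2. In SAP sections 11.3.1.1 and 11.3.1.6 to 11.3.1.8, name the reading and scale that feed TMS, MMS, remission and response at BIS, BOLS, M2, M12, M24, M36 and M48.
3. Use the central reading for clinical remission at M24, M36 and M48, as the protocol defines it. Report local-reading results, including M12, as a separate series, with the reader and scale in each table footnote.
4. Do not compute change or sustained status across different scales. Use the same reader and scale at both ends where the BIS and BOLS readings allow; otherwise label the result as crossing scales.
5. Add the acceptance of local readings for remission to SAP section 1.2.

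The cost is SAP wording and one extra table block, drawn from sub-scores already planned for Listing 16.2.6.1. No new patient assessment is needed. The downside is two endoscopic series to present. Some changes from baseline may also not be computable on one scale, since a matching BIS or BOLS reading may not exist and must be confirmed first.
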